Objectives	
Primary: Assess the effect of CCT versus waiting list control on global cognition in multi-domain MCI with sleep disturbance.
 
Global cognition definition: pre-specified summary z-score composite across 5 cognitive domains of: memory, attention, executive function, processing speed, language.
 
Secondary:
 
 1. Does the immediate therapeutic cognitive effect differ if training commenced immediately or 3-months later? 2. Does the cognitive state 9-months after entering the trial differ if CCT was commenced immediately or 3-months later? 3. Change in individual cognitive domains measured in separate summary z-score composites 4. Change in daily functional: ADCS-ADL-Prevention Questionnaire 5. Change in quality of life: WHOQOL 6. Change in mood and mental-health symptoms: 15-Item GDS 7. Change in sleep-wake patterns: Sleep diary, actigraphy, PSQI 8. Change in risk-perception: Economic Decision Making Competency tool 9. Predictors of cognitive response to CCT: APOE 3/4 and BDNF ValMet polymorphism and baseline cognitive profile.
Study Design	Randomised, controlled, double-blinded, clinical trial
Planned Sample Size	62
Selection Criteria	Older adults (aged 50 or older) with amnesic multi-domain MCI with sleep disturbance:
Study Procedures	
The trial is divided into three 3-month phases with three separate objectives (see Figure 3)
 
Phase I is a 12-week randomised, double-blinded, wait-list controlled trial that will follow CONSORT¹ and SPIRIT² guidelines and follow Good Clinical Practice recommendations³.

	
Subjects will be randomly allocated in a 1:1 ratio to either 3-months of supervised, centre-based, multidomain CCT (ARM A) or wait-list control. The main endpoint from Phase I will be to determine whether CCT is effective for improving overall cognition for those with multidomain MCI with sleep disturbance. This is the trial’s primary outcome.
 
The Phase II endpoint is to assess whether the magnitude of therapeutic effect is dependent on the onset of treatment. Arm A started CCT 3-months prior and will transition to no-contact follow-up for 3-months, whilst Arm B that was on-hold for 3-months will commence the identical CCT intervention that Arm A completed in Phase I.
 
The endpoint for Phase III is to determine whether delayed start of CCT matters after a period of no-contact follow up. The trajectory of cognitive function following early intervention versus delayed intervention will be examined. Both groups will receive no intervention for a further 3 months, with the main difference being that Arm A halted CCT 3-month previously whilst Arm B started CCT 3-months later. In order to assess the effect of delayed start separately from waning of benefits, Arm A at the end of Phase I will be compared to Arm B at the end of Phase II. Arm A at the end of Phase II will also be compared to Arm B at the end of Phase III to investigate the effect of delayed start on longevity of the intervention.
 
Cognitive assessment will be completed at baseline and at the end of each phase.

Statistical Procedures Sample Size Calculation: Analysis Plan:
	
 • Phase I: An intention-to-treat approach using recommended Linear Mixed Modelling⁴ will evaluate a model including main effects for Group (Arm A vs Arm B), Time (BL vs FU1) and the main interaction term of interest: Group X Time. Covariates will only be added if baseline differences are noted between groups. • Phase II Linear Mixed Modelling⁴ will evaluate a model including main effects for Group (Arm A vs Arm B), Time (Arm A BL vs FU1, Arm B FU1 vs FU2) and the main interaction term of interest: Group X Time

	
 • Phase III: T-test between Arm A vs Arm B at FU3. • Clinical Response Prediction will be addressed by multiple regression examining relationships between baseline predictor variables (i.e; cognitive profile) and cognitive change scores. • Sample Size and Power This study is powered on the basis of a relative effect size (RES) on Global Cognition of 0.44 at the end of the Phase I RCT (based on average from our Timecourse Trial⁵ and NHMRC SMART trial⁶). Designate power of 0.80 controlling α at 0.05 translates to a required sample size of N=52 (calculated using G*Power 3.1 based on ANOVA repeated measures within-between interaction test, 2 groups, 2 time-points, within subject autocorrelation =0.4, equivalent effect size of [v]=0.22). A sample of N=62 (rounded up from 61) will be recruited to allow for 15% overall attrition (as per Timecourse Trial extrapolated to 9-months).
Duration of the study	3 years

GLOSSARY OF ABBREVIATIONS

ABBREVIATION	TERM
CCT	Computerised Cognitive Training
MCI	Mild Cognitive Impairment
BTS	NHMRC Maintain Your Brain Trial Brain Training System
ADCS-ADL	Alzheimer’s Disease Cooperative Study-Activities of Daily Living
WHOQOL	World Health Organisation Quality of Life
GDS	Geriatric Depression Scale
PSQI	Pittsburgh Sleep Quality Index
APOE 4	Apolipoprotein E 4
BDNF	Brain-derived neurotrophic factor

1.4 Internal Trial Committees

Researchers: [name], [name], Statistician: [name], Co-ordinator: [name]

1.5 Independent Safety and Data Monitoring Committee: not applicable as intervention is entirely safe. There has never been an adverse event incident in any of the cognitive training trials that [name] has led or been associated with and none reported in meta-analyses or individual studies (more than 75 trials to date).

1.6 Sponsor

University of Sydney NSW 2006

1.7 Funding and Resources

Funded by an NHMRC Project Grant (ID1084880, [name]), \$715,764

2. INTRODUCTION AND BACKGROUND

2.1 Background information

Dementia and Alzheimer's: a global priority

Dementia is a disorder with huge global economic burden as currently, 47 million people suffer from it and the prevalence is expected to increase to more than 131 million by 2050. The 2016 total estimated worldwide cost of dementia is USD 818 billion, approaching a trillion-dollar disease by 2018⁷. There are no effective treatments as yet, to combat or alter the course of dementia. It is therefore highlighted from the G7-led Global Action on Dementia that the development of such treatments is an inter-governmentally agreed global public health priority⁸.

Clinicians have long delineated a prodromal condition with cognitive symptoms prior to the onset of dementia and Alzheimer's disease (AD). This condition is known as Mild Cognitive Impairment (MCI). Individuals in this clinical staging present with subjective cognitive complaints and/ or objective evidence of abnormal cognitive testing with no functional deficits associated with cognitive impairment. Whilst not all rigorously defined MCI patients progress into dementia or AD and can revert back to normal, the rate of progression to AD is highest, while the rate of reversion is lowest⁹.

Modifiable risk factors for prevention

Cognitive inactivity is estimated to be the most prevalent modifiable dementia risk factor worldwide¹⁰. [name] has hence advanced a research program around an active cognitive lifestyle, characterised by a lifelong pattern of engagement in complex mental activities such as advanced and ongoing education, participation in mentally-challenging occupations, maintenance and development of social networks and pursuit of cognitively-loaded hobbies and pastimes¹¹. Our meta-analysis of 18 prospective longitudinal studies found high levels of complex mental activity was associated with a 46% decreased risk of incident dementia¹². Similarly, a systematic review based on aggregated data of 47,000 individuals followed for an average of 5 years revealed that lifespan complex mental activity slows the rate of cognitive decline in otherwise healthy older individuals¹³.

MCI has been associated with comorbid neuropsychiatric conditions similar to that of dementia and AD. Multiple studies have shown that depression, lack of motivation and anxiety are more prevalent in MCI individuals than in cognitively intact people. Further, both major depression and anxiety markedly increased the risk of MCI conversion into Dementia^{14,15}. There is also increasing evidence to

suggest that sleep quality also plays an important role in cognitive health in ageing. A review has revealed that people with MCI are almost twice as likely to have sleep disturbance than those with normal cognition (18.3-45.5% compared to 10.9-23.3%, respectively)¹⁶. This study also provides evidence to suggest that sleep disturbance is predictive of cognitive decline in older adults and those with neurodegenerative disorders. It has been identified that changes in sleeping patterns occur in MCI in the form of poor sleep efficiency, fragmented sleep, increased frequency of daytime napping, propensity to fall asleep and wake up earlier, and decreased levels of slow wave sleep. In AD, there are the same alterations in sleeping patterns, but to a higher intensity. One positive aspect of these knowledge combined, is that these are modifiable and manageable risk factors that contribute to hastened cognitive decline.

Therefore, by treating these modifiable risk factors, we hypothesise that this may help prevent against the development of dementia and AD. One such intervention that is able to target these risk factors is Computerised Cognitive training (CCT)

CCT

CCT is a cognitive intervention that uses computerised platforms including audiovisual stimuli, videogames or virtual reality. It involves repeated exercises on one or multiple cognitive domains such memory, executive functions or processing speed. The advantages of using this intervention is that it is safe, scalable, versatile, adaptive, and relatively inexpensive.

In a meta-analysis of MCI trials conducted by our group¹⁷, CCT was efficacious not only for global cognition ($g=0.38$, 95%CI: 0.14-0.68) but also for psychosocial functioning ($g=0.52$, 95%CI: 0.01-1.03; $k=17$ RCTs, $N=686$).

To date, an individual RCT has shown that CCT improved both sleep quality (sleep onset latency and sleep efficiency) and cognitive performance (memory, working memory, and attention) in cognitively-intact older adults with insomnia¹⁸.

The timing of therapeutic gains in CCT is also of interest. In our Timecourse Trial⁵, we revealed that CCT progresses through three distinct therapeutic phases: loading dose, where there is a rapid onset of therapeutic gains, plateau, where therapeutic gains begin to reduce with additional training and reach maxima, and maintenance, where after cessation of training therapeutic gains wane quickly but some residual benefits are maintained in the long term. Whilst these temporal characteristics have been described assuming all patients begin CCT at a given time, it is unknown what the impact delaying the start of treatment in MCI may have. This is particularly important given: a) cognitive decline is more rapid in MCI than in healthy elderly, suggesting that timely intervention is required, and b) there is a common practical resource barrier such that not all those with MCI may be able to access CCT at a given time (in effect creating a waiting-list). Accordingly, whether CCT therapeutic gains degrade over time in

MCI is clinically important, as is whether this matters over the longer term after the cessation of training.

In summary, there have not yet been any studies to test the efficacy of CCT in multi-domain MCI patients with concomitant sleep disturbance, and no studies have systematically investigated the impact of timing of onset of treatment.

2.2 Main Research Questions

- a. What are the effects of CCT on global cognitive function in multi-domain MCI with sleep disturbance?
- b. In this population, are delayed training effects equivalent to immediate training effects?
- c. In this population, does starting training early compared to later change outcome after cessation of training?
- d. In this population, does CCT help with sleep symptoms?
- e. In this population, does CCT transfer to important functional outcomes such as IADLs, psychosocial state and decision making?
- f. Is there a cognitive response phenotype?
- g. Does APOE or BDNF ValMet polymorphisms influence cognitive responsivity?

2.3 Rationale for Current Study

This RCT will produce three main endpoints:

Firstly, it will determine whether CCT is effective for improving global cognition, thereby providing a potential intervention for the reversal of cognitive decline and prevention of developing dementia for those at high-risk.

The prevalence of MCI is even higher than that of dementia¹⁹. Small gains could have a major impact on prevention of disease burden: a 2-year delay in dementia presentation would for example reduce the prevalence of the disease by 20% by shifting symptom onset (at a population level) beyond natural mortality. With no current effective treatment for dementia and Alzheimer's disease, this endpoint therefore has major significance to human-health, particularly with respect to age-related disease burden.

Secondly, we will learn whether CCT produces secondary gains across a wide variety of important clinical outcomes, including day-to-day function, mood, and quality of life. In particular, assess the impact of CCT on sleep quality in those with sleep disturbance (the first time in MCI). This will also further support the RCT which found CCT improved sleep for participants with disturbed sleep¹⁸ (albeit without MCI). This endpoint will translate to clinically- and personally-relevant information.

Thirdly, this RCT will clarify if the timing of onset of CCT in this clinical population matters. This is of great pragmatic importance, as not all MCI patients can access in-person CCT at the same time.

Fourth, this RCT will examine for the first time in this population if there biological (genetic) or cognitive (profile) predictors of therapeutic response, of great significance for the more selective application of this treatment in MCI and for better resource allocation at a community level.

Accordingly, this endpoint will add fundamental new knowledge highly relevant to clinical practice. Flowing from these endpoints is the expectation of top-quality publications in international peer-reviewed journals, as well data that will directly inform future guidelines for the use of BT in the clinic and in the community. Overall, the outcomes from this project are suggested to be of international medical, scientific and community significance.

3. STUDY OBJECTIVES

3.1 Primary Objective

To assess the effect of CCT versus waiting list control on global cognition in multi-domain MCI with sleep disturbance.

Global cognition definition: pre-specified summary z-score composite across 5 cognitive domains of: memory, attention, executive functions, processing speed, language.

3.2 Secondary Objectives

Determine the following:

1. Does the therapeutic cognitive effect differ if training commenced immediately or 3-months later?
2. Does the cognitive state 9-months after entering the trial differ if CCT was commenced immediately or 3-months later?
3. Change in individual cognitive domains measured in separate summary z-score composites
4. Change in daily functional: Amsterdam IADL
5. Change in quality of life: WHOQOL
6. Change in mood and mental-health symptoms: 15-Item GDS
7. Change in sleep-wake patterns: Sleep diary, actigraphy, PSQI
8. Change in risk-perception: Economic Decision Making Competency tool
9. Predictors of cognitive response to CCT: APOE 3/4 and BDNF ValMet polymorphism and baseline cognitive profile.

3.3 Background Variables

The following variables will be tested at baseline for any systematic differences between randomisation groups as well as for associations with change in primary and secondary outcomes: age, sex, education, WTAR, physical activity (using CHAMPS questionnaire), SF-36 physical health, cardiovascular risk factors, cognitive lifestyle (using [name]'s Lifetime of Experiences Questionnaire), PSQI²⁰, family history of dementia, APOE4 and BDNF status, new onset illness or new medication use.

4. STUDY DESIGN

4.1 Type of Study

This study is a 9-month randomised, double-blind, passive-controlled clinical trial that will explicitly follow CONSORT¹ and SPIRIT² guidelines and follow Good Clinical Practice recommendations³.

4.2 Study Design

This clinical trial adheres to the conceptual and ethical framework for prevention trials articulated by Peters et al, in which long-term intervention in individuals at-risk for dementia should be correspondingly low-risk²¹. Our experience across four major longitudinal RCTs of CCT has been of no adverse events.

MCI clients that meet basic entry criteria will be recruited from the Healthy Brain Ageing (HBA) clinic, Brain and Mind Centre, University of Sydney (head: [name]) and the Memory Clinic of the Prince of Wales Hospital (head: [name]). Any additional assessments required beyond clinic-based tests, and all intervention procedures, will take place at the Brain and Mind Centre, Sydney, Australia.

The study will consist of three phases and follow-up assessments designed to produce distinct outcomes (refer to **Figure 3**).

Subjects will be randomly allocated in a 1:1 ratio to either ARM A: immediate intervention or ARM B: delayed intervention. Those in ARM A will commence supervised, centre-based multi-domain CCT twice a week, 1 hour per session for 3 months. The main endpoint at the end of Phase I will be to determine whether CCT can improve cognitive function in comparison to a waitlist control. For ARM A, we hypothesize that CCT will lead to an improvement in global cognition. For ARM B, we hypothesise that there will be no change in cognition or measureable cognitive decline. On the basis of our previous work in the Timecourse Trial⁵ and NHMRC-funded SMART Trial³⁸, our proposal is powered for Phase 1 (baseline-FU1) of the trial.

The endpoint of FU2 is designed to assess the magnitude of effect between immediate intervention versus delayed intervention (see Figure 3 and 4). That is, whether the effect size of CCT for ARM B is equivalent to the effect size of CCT for ARM A. We hypothesise that the effect size for those allocated in ARM A will

be greater than ARM B. This is because, as time progresses, the abnormality rates for cognition and other dementia and AD biomarkers increases, thereby making it more difficult to treat. (Figure 1,2)³⁹

Figure 1

[figure not shown]
[figure not shown]
[figure not shown]

Figure 2

The endpoint of FU3 will assess the long-term implication of immediate compared to delayed intervention. If over a 9-month period the timing of a 3-month CCT intervention does not matter, i.e., both arms are cognitively equivalent at the end, then that may influence and inform the distribution of CCT resources in clinics and the community.

Figure 3: Study Hypotheses

Hypotheses

es = effect size

e = endpoint

Primary

Phase I: $es_{A1} > es_{B1}$

Secondary

Phase II: $es_{A1} > es_{B2}$

Phase III: $e_{A3} = e_{B3}$

Assess for eligibility:
Multi-domain MCI criteria
Sleep disturbance criteria
No major neurological/psychiatric/mood disorder

Exclude:
Not meet inclusion criteria
Declined to participate

Written Consent

Enrolment

Baseline Measurements:

- Neuropsychological tests
- Sleep-wake quality
- DNA saliva swab
- Economic decision making

Randomised (n=62)

ARM A
(n=32)

Allocation

ARM B
(n=32)

- Neuropsychological outcomes
- Sleep-wake quality
- Neuroimaging
- Economic decision making
- Review for any adverse events
- Lost to follow-up (reasons)

Follow-up 1
3-months after baseline

- Neuropsychological outcomes
- Sleep-wake quality
- Neuroimaging
- Economic decision making
- Review for any adverse events
- Lost to follow-up (reasons)

- Neuropsychological outcomes
- Sleep-wake quality
- Review for any adverse events
- Lost to follow-up (reasons)

Follow-up 2
6-months after baseline

- Neuropsychological outcomes
- Sleep-wake quality
- Review for any adverse events
- Lost to follow-up (reasons)

- Neuropsychological outcomes
- Sleep-wake quality
- Review for any adverse events
- Lost to follow-up (reasons)

Follow-up 3
9-months after baseline

- Neuropsychological outcomes
- Sleep-wake quality
- Review for any adverse events
- Lost to follow-up (reasons)

- Intention-to-treat analyses: Linear Mixed Model
- Clinical response prediction: Multiple regression
- Excluded from analysis (reasons)

Analysis

- Intention-to-treat analyses: Linear Mixed Model
- Clinical response prediction: Multiple regression
- Excluded from analysis (reasons)

Screening

MCI criteria

MCI is diagnosed according to the Winblad et al 2004 criteria²² confirmed on the basis of consensus rating of multiple clinicians within the memory center.

Typically, this includes a geriatrician or neurologist and two clinical neuropsychologists who review the individual's clinical profile and neuropsychological results.

The Winblad 2004²² recommends the diagnosis of MCI to fulfil the following criteria: 1. The individual does not meet the criteria for a dementia syndrome in accordance to the DSM IV or ICD 10; 2. Functional activities of the person are mainly preserved; 3. Evidence of cognitive decline.

Objective cognitive impairment is defined as performance of more than or equal to 1.5 standard deviation below the patient's estimated level of premorbid general intellectual functioning (determined using the Wechsler Test of Adult Reading²³).

Cognitive domains are defined based on the following:

Memory: Wechsler Adult Intelligence Scale (WAIS) Digit Span²⁴; Rey Auditory Verbal Learning Test²⁵; Wechsler Memory Scale-III Logical Memory I²⁶ and II²⁷,

Learning: Rey Complex Figure Test-3 minute Recall²⁸,

Speed of processing: Trails Making A²⁹

Language: Controlled Oral Word Association Test³¹; Boston Naming Test³¹

Visuospatial skills: Rey Complex Figure Test-Copy²; Clock-drawing Test³³

Executive functioning: Delis Kaplan Executive Functioning System^a (STROOP)³⁴; Trails Making B²⁹;

Daily function: Amsterdam IADL (informant-rated if available)³⁴, Global Deterioration Scale³⁵; Global assessment of Functioning Scale³⁷

Where possible, alternate forms are used between assessments to reduce retest effects.

Single domain MCI refers to MCI with impairment in only one domain; if more than one domain is affected, it is defined as **multi-domain MCI**. Amnesic MCI is defined here by an impairment in delayed recall (assessed as Logical Memory II total score or percent retention²⁷; Rey Auditory Verbal Learning Test trial 7 total score or 7/5 percent retention²⁵). In cases where only new learning is impaired but delayed recall is intact, the individual is categorised as non-amnesic MCI.

Sleep disturbance criteria

Sleep disturbance will be measured with the Pittsburg Sleep Quality Index (PSQI)²⁰: Self Report Questionnaire. Patients with multi-domain MCI diagnosed with the above criteria and a score of ≥ 5 in the PSQI; without any major neurological or psychiatric disorder, major depression, current alcohol abuse, will be eligible for the study.

^a If this test data is not available/provided by the referral memory clinic we will conduct the test after consent and prior to commencement of the intervention

Randomisation

Randomisation will be by computer-generated sequence using small block sizes (n=2), administered by [name]. Allocation will be revealed to the Study Coordinator after the completion of each baseline assessments. A small block size will ensure that the immediate intervention will start relatively immediately.

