10.3 Statistical Analysis Plan

Phase I: An *intention-to-treat* approach using recommended Linear Mixed Modelling⁴ will evaluate a model including main effects for Group (Arm A vs Arm B), Time (BL vs FU1) and the main interaction term of interest: Group X Time. Covariates will only be added if baseline differences are noted between groups.

Phase II Linear Mixed Modelling⁴ will evaluate a model including main effects for Group (Arm A vs Arm B), Time (Arm A BL vs FU1, Arm B **FU1 vs FU2**) and the main interaction term of interest: Group X Time. An additional covariate of initial global cognitive status will be added to this analysis to control for different potential starting points for the two arms at the different timepoints.

Phase III: Equivalence of the two arms at follow up III will be tested using a two one-sided test (TOST⁴²).

Clinical Response Prediction will be addressed by multiple regression examining relationships between baseline predictor variables (i.e; cognitive profile) and cognitive change scores.

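### Phase III reads equal scores at FU3 as showing that the timing of CCT is unimportant, but the arms are then 6 and 3 months past training, so FU3 alone cannot support that conclusion

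*Protocol*

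**What the plan says.** Section 4.2 gives the meaning of the FU3 endpoint: "If over a 9-month period the timing of a 3-month CCT intervention does not matter, i.e., both arms are cognitively equivalent at the end". It adds that such a result may guide the allocation of CCT in clinics and the community. The hypotheses listed there predict a larger training effect in Arm A during Phase I than in Arm B during Phase II, and equal endpoints at FU3.

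The Phase III analysis in section 10.3 is: "Equivalence of the two arms at follow up III will be tested using a two one-sided test". The synopsis names a t-test at the same visit. That discrepancy is a separate matter; both use FU3 only.

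On Phase III, the synopsis (Study Procedures) says: "Both groups will receive no intervention for a further 3 months, with the main difference being that Arm A halted CCT 3-month previously". On waning, section 2.1 reports from an earlier trial that "after cessation of training therapeutic gains wane quickly but some residual benefits are maintained in the long term".

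The synopsis also anticipates the difficulty. It says "In order to assess the effect of delayed start separately from waning of benefits, Arm A at the end of Phase I will be compared" with Arm B at the end of Phase II, and then "Arm A at the end of Phase II will also be compared to Arm B at the end of Phase III". Section 10.3 carries the first of these as the Phase II model, which contrasts change from baseline to FU1 in Arm A with change from FU1 to FU2 in Arm B, adjusted for initial cognition. The second is in neither statistical section.

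Two questions bear on FU3. Research question (c) in section 2.2 asks: "does starting training early compared to later change outcome after cessation of training". Secondary objective 2 in section 3.2 is narrower: whether cognitive status nine months from entry differs between the schedules.

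**The concern.** At FU3 the arms differ in two respects: when training began, and how long ago it stopped. If gains fade after training, the second difference favours the delayed arm. It can offset a weaker response to delayed training, or give Arm B a lead when delay did no harm to the response.

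The protocol predicts a weaker response in the delayed arm and equal scores at FU3. If both predictions came true, Phase II would show that delay reduced the response, while section 4.2 would have the FU3 result read as timing making no difference. That reading is meant to inform waiting-list practice. The primary Phase I comparison is not affected.

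**Working it through.** **The plan's own figure.** The only effect size given is 0.44 (f = 0.22, section 10.1), used for Phase I. The noncentrality is f²·N·m/(1 − ρ) = 0.0484 × 52 × 2/0.6 = 8.39 on 1 and 50 degrees of freedom. This gives power 0.811; N = 50 gives 0.795. So N = 52 reproduces, and 52/0.85 = 61.2 gives 62. Nothing here turns on that calculation; 0.44 SD serves below only as a scale.

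**Time since training at FU3.** Arm A trains in months 0–3, so 9 − 3 = 6 months. Arm B trains in months 3–6, so 9 − 6 = 3 months.

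**Decomposition.** Let E be the gain at the end of immediate training, L the fraction of it lost through delay, and r3 and r6 the shares retained 3 and 6 months after training. Natural decline and retest effects are taken as equal in the two arms at a common visit.

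- FU3, A − B = E·r6 − (1 − L)·E·r3. This is zero when L = 1 − r6/r3.
- First matched comparison, A at FU1 − B at FU2 = E·L.
- Second matched comparison, A at FU2 − B at FU3 = E·r3·L.

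The matched formulas leave out any change due only to time from entry or repeated testing.

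**Numbers.** E = 0.44 SD. The retention values are assumptions, because the protocol describes waning only in words.

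| r3, r6 | FU3 contrast if L = 0 | L that gives zero at FU3 | First matched, at that L | Second matched, at that L |
|---|---|---|---|---|
| 0.5, 0.4 | −0.044 | 20% | 0.088 | 0.044 |
| 0.8, 0.6 | −0.088 | 25% | 0.110 | 0.088 |
| 0.5, 0.25 | −0.110 | 50% | 0.220 | 0.110 |
| r3 = r6 > 0 | 0 | none | – | – |

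For the third row: L = 1 − 0.25/0.5 = 0.5, and the FU3 contrast is 0.44 × 0.25 − 0.5 × 0.44 × 0.5 = 0.11 − 0.11 = 0. In the first three rows FU3 shows zero while both matched comparisons stay positive.

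**Why the mean over FU1–FU3 is no substitute.** It counts Arm B's untreated FU1, so it favours Arm A whenever CCT works.

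- No delay loss and no waning: A = (0.44 + 0.44 + 0.44)/3 = 0.440; B = (0 + 0.44 + 0.44)/3 = 0.293; difference 0.147.
- Half the response lost, with retention 0.5 then 0.25: A = (0.44 + 0.22 + 0.11)/3 = 0.257; B = (0 + 0.22 + 0.11)/3 = 0.110; difference 0.147.

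The two situations give the same answer.

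**The case against.** **The protocol sees the problem.** A reader might infer that waning was overlooked and that the timing question rests on FU3 alone. It does not. The synopsis sets out to separate delay from waning, and section 10.3 analyses the end-of-training contrast as Phase II. A SAP, which is not shown, may also specify the second comparison. This stands and narrows the point. What remains is that section 4.2 itself fixes the conclusion on FU3, with no reference to either matched comparison.

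**FU3 is a proper randomised contrast.** One might call it confounded and any Arm B lead false. But both arms are measured at the same time from entry, and recency is part of the delayed schedule. An Arm B lead would be a real effect of the schedule on 9-month status, which is what secondary objective 2 asks. The fault lies only in the wider reading. It is also fair that section 4.2 refers to the end of a 9-month period and says only that the result may inform resources.

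**The two hypotheses need not conflict.** It is tempting to say they can both hold only if waning exactly cancels the delay loss. That is wrong: scores at FU3 are also equal if gains vanish completely, or if both arms settle at the same residual level.

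**The distortion depends on the shape of waning.** Section 2.1 describes a quick fall with some benefit kept. If most of the fall comes within 3 months, r3 and r6 are close and the distortion is small. Nor would an Arm B lead defeat equivalence at every margin: a lead of 0.11 SD lies inside any wider margin. Both limits stand.

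**Conclusion.** The point holds in a limited form. Equivalence at FU3 supports a statement about cognitive status nine months after entry under the two schedules. By itself it does not support the statement that timing is unimportant, because the arms differ by 3 months in time since training.

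The weakness requires that gains still fade between 3 and 6 months after training. Under the assumed retention values, a delay loss of 20% to 50% would be invisible at FU3, and no delay loss would appear as an Arm B lead of 0.044 to 0.11 SD. These figures illustrate the direction and possible scale; they are not estimates for this trial. The documents do not support calling FU3 invalid, or stating any particular loss as hidden.

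**What to change.** - In section 4.2, limit the FU3 conclusion to cognitive status at 9 months under each schedule, and state beside it that Arm A is then 6 months and Arm B 3 months past training.
- Add the comparison of Arm A at FU2 with Arm B at FU3 to section 10.3.
- Allow a statement that timing is unimportant, or one on distributing CCT, only when FU3 is read together with both matched comparisons.
- State the limits of those comparisons. They are made at different times from entry (3 against 6 months, and 6 against 9) and after different numbers of test sittings, so natural decline and retest effects can enter.
- Report them with confidence intervals. With 52/2 = 26 per arm and an SD of 1 (assumed), the standard error of a simple difference is √(2/26) = 0.28 SD, above every value in the table. A non-significant result would not show that delay costs nothing.
- Do not rest the timing conclusion on the mean over FU1–FU3.

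The cost is wording, a narrower Phase III claim and one further comparison. Section 7 already schedules the cognitive tests at FU2 and FU3.
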